### 1.4.6 Day of last dose of study treatment

The date of last dose will be collected via the eCRF. The subject's extent of exposure will be calculated considering the end of treatment period visit (e.g., Treatment Period 1 completion visit). If a subject discontinued early, then the last visit during the treatment period is considered (e.g., last visit in Treatment Period 1, if subject discontinued from Treatment Period 1).

# 1.5 Subject disposition, background and demographic characteristics

#### 1.5.1 Subject disposition

The total number of subjects screened and of subjects in the SAF-TP1 set will be presented. In addition, the reasons for screen failures will be provided.

The number and percentage of subjects in the SAF-TP1 who completed Treatment Period 1 and who discontinued the study prematurely (including the reason for discontinuation) in this period will be presented.

The number of patients in the SAF-TP2 and the numbers of patients in the FAS-P90R set and in the FAS-P75R set will be provided. The numbers and percentages of subjects in the FAS-P90R and in the FAS-P75R who completed Treatment Period 2 and who discontinued the study prematurely (including the reason for discontinuation) in this period will be presented. Furthermore, the numbers of patients in the PP-P90R, PP-FUS and in the FUS will be presented.

Reportable protocol deviations as defined in the final protocol deviation (PD) Edit Check Specification will be presented in terms of absolute numbers and percentages separately for each study period (Treatment Period 1, Treatment Period 2, Follow-Up Period) for the SAF-TP1, the FAS-P90R and the FAS-P75R.

#### 1.5.2 Background and demographic characteristics

The following common background and demographic variables will be analyzed:

- Age (which is derived from date of birth and the date of screening visit)
- Age categories (<65 years,  $\ge 65$  years and <75 years,  $\ge 75$  years)
- Gender
- Race

- Height
- Weight at Baseline
- Weight categories at Baseline (< 90kg, ≥ 90kg)

- Body mass index at Baseline (BMI)
- Smoking status at screening visit (never, current, former)
- Smoking amount: estimated amount consumed (in pack years) for current smokers
- Time since stop of smoking until screening visit (years)
- Tuberculosis (TB) status at Baseline (no TB present, active TB diagnosed, latent TB diagnosed)
- Initiation of TB therapy according to local guidelines (yes, no) for patients with latent TB

The Body Mass Index (BMI) at Baseline will be calculated using the following formula:

BMI 
$$(kg/m^2) = (body weight in kilograms at V2) / (height in meters)^2$$

For BMI, the body weight used is the last value prior to treatment start. If there is no weight recorded prior to taking of study treatment, BMI will be missing.

Psoriasis specific baseline characteristics and history of disease will be summarized as well:

- Baseline PASI
- Baseline PASI categories ( $\leq 20, \geq 20$ )
- Baseline IGA mod 2011 score (almost clear, mild disease, moderate disease, severe disease)
- Body Surface Area (BSA) affected by plaque-type psoriasis at baseline
- Time since occurrence of plaque psoriasis (years between start date and date of screening visit)
- Presence of psoriatic arthritis
  - time since occurrence of psoriatic arthritis (years between start date and date of screening visit)

Unless otherwise specified, summary statistics will be presented for continuous variables for all subjects in the SAF-TP1 and for each treatment group and for all subjects (total) in the FAS-P90R and the FAS-P75R.

The number and percentage of subjects in each category will be presented for categorical variables for all subjects in the SAF-TP1 and for each treatment group and for all subjects (total) in the FAS-P90R and the FAS-P75R.

Smoking history will be analyzed separately for former and current smokers. No statistical tests for comparability of baseline characteristics will be performed.

#### 1.5.3 Medical history and current medical conditions

Analyses will be based on all subjects in the SAF-TP1 and on the FAS-P90R and the FAS-P75R by treatment group and overall.

Any condition entered on the *Relevant medical history/current medical conditions* eCRF will be coded using the MedDRA dictionary. They will be summarized by System Organ Class (SOC) and Preferred Term (PT) of the MedDRA dictionary. *Cardiovascular medical history* will be summarized by the categories provided in the eCRF separately for prior and ongoing terms.

### 1.6 Study medication

The analysis of study treatment data during Treatment Period 1 will be based on the SAF-TP1 and during Treatment Period 2 on the FAS-P90R and the FAS-P75R.

The number of administered injections will be summarized for all patients in the SAF-TP1 and by treatment group in the FAS-P90R and the FAS-P75R according to the methods described in Section 2.1 (continuous data) and Section 2.2.1 (categorical data).

Compliance will be calculated in percent separately for both treatment periods, as the number of injections administered divided by the number of injections scheduled according to the protocol.

Duration of exposure will be defined as the time (in days) from first dose of study medication in a treatment period to the day of the last dose of study treatment in the respective treatment period (section 1.4.6).

The duration of exposure to study treatment will be summarized for all patients in the SAF-TP1 and by treatment group in the FAS-P90R and the FAS-P75R. In addition, the number of subjects with exposure of at least certain time thresholds will be displayed. The following categories will be presented for Treatment Period 1: "any exposure", "≥1 week" (i.e. "≥7 days), "≥2 weeks" (i.e. ≥14 days), "≥3 weeks" (i.e. ≥21 days), "≥4 weeks" (i.e. ≥28 days), "≥8 weeks" (i.e. ≥56 days), "≥12 weeks" (i.e. ≥84 days), "≥16 weeks" (i.e. ≥112 days) and "≥20 weeks" (i.e. ≥140 days).

For Treatment Period 2 exposure categories in terms of 2-weeks intervals will be presented for the SAF-TP2: starting with "any exposure", " $\geq$ 2 weeks" (i.e.  $\geq$ 14 days), " $\geq$ 4 weeks" (i.e.  $\geq$ 28 days), " $\geq$ 6 weeks" (i.e.  $\geq$ 42 days), " $\geq$ 8 weeks" (i.e.  $\geq$ 56 days) up to " $\geq$ 24 weeks" (i.e.  $\geq$ 168 days).

The amount of observed "patient years" will be calculated as sum of all subject-times (in days) divided by 365.25 for both treatment periods.

#### 1.7 Prior and concomitant medication

Medications will be identified using Novartis Drug and Therapy Dictionary (NovDTD) including Anatomical Therapeutic Chemical (ATC) code.

Prior and concomitant medications will be summarized in separate tables for all patients in the SAF-TP1 and by treatment group in the FAS-P90R and the FAS-P75R. In the SAF-TP1

concomitant medication will be only displayed for Treatment Period 1, in the FAS-P90R and FAS-P75R only concomitant medication from Treatment Period 2 will be presented.

Prior medications are defined as drugs taken and stopped prior to first dose of study treatment. Any medication given at least once between the day of first dose of study treatment and the last day of Treatment Period 2 will be a **concomitant** medication, including those which were started pre-baseline and continued into the Treatment Period 1. Medication with start date prior to Baseline and without end date will be considered as concomitant medication. Medications starting at the last day of Treatment Period 1 will be considered as concomitant medication for Treatment Period 2. Incomplete start and/or stop dates (e.g. only the year) of medication are supposed to lie before the date of first dose of study treatment.

Medications will be presented in alphabetical order, by ATC codes and grouped by *anatomical main group* (the 1st level of the ATC codes). Tables will show the overall number and percentage of subjects receiving at least one drug of a particular ATC code and at least one drug in a particular anatomical main group.

Specific summaries of prior and/or concomitant medication will be presented for the categories of previous psoriasis therapy presented in Table 1-4.

In addition, medical procedures and significant non-drug therapies as coded in MedDRA will be summarized.

Table 1-4 Categories of previous psoriasis therapy

Level 1 description	Level 1 outcome	Level 2 description	Level 2 outcome
previous	no		
psoriasis	yes	failure**	1
therapy			2
			>=3
			no
			yes

only selected subgroups will be used for reporting

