The main purpose of this Amendment is to align the requirements for the duration of contraception to be used by patients during the study with the approved European Summary of Product Characteristics. According to the Exclusion criteria (Section 4.2) of the study protocol women of childbearing potential must use effective methods of contraception during dosing of study treatment and for 16 weeks after stopping treatment, in line with phase III AIN457A program study protocols.

Therefore the advice to female patients to prevent pregnancy is amended to cover also the contraception length post treatment requirements of the European Summary of Product Characteristics (20 weeks).

In addition, the approved European Summary of Product Characteristics specifies for the prefilled secukinumab syringe a warning and precaution for use in case a latex sensitivity would be pertinent for a patient. The removable needle cap of the pre-filled syringe contains a derivative of natural rubber latex; no natural rubber latex has to date been detected in the removable needle cap. Nevertheless, the use of pre-filled syringes in latex sensitive individuals has not been studied and there is therefore a potential risk of hypersensitivity reactions which cannot be completely ruled out. The Exclusion criteria (Section 4.2) of the study protocol have been updated accordingly, as well as the Risks and benefits (Section 3.6).

Other sections have been updated to provide clarity.

Changes to the protocol

The main changes made to the protocol are:

- Protocol synopsis: updated to reflect the changes in the main protocol text
- Section 4.2 exclusion criterion 3 and the Risks and benefits (Section 3.6) are revised to include also latex hypersensitivity
- Section 4.2 exclusion criterion 8 is revised to align post treatment contraception length with the EU Summary of Product Characteristics
- Section 6 updated content, incl. Table 6-1, to clarify details for the laboratory assessments, clarify that the 5 response level EQ-5D Health Status Questionnaire is used, and that Chest X-ray (or CT/MRI) is recorded on source documentation
- Section 6.2.5 is updated to include a statement on Crohn's disease

The first patient was recruited in the study on 12 June 2015 and around 11 of 1580 planned patients have been treated with study medication during finalization of the protocol amendment.

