#### 2.3 Analysis of time-to-event data

Number and percentage of subjects with a clinical event based on the number of subjects in the analysis set at risk as denominator will be provided by treatment group.

For each time-to-event variable, between-treatment differences will be evaluated using a logrank test, stratified by country and weight at Week 24 (<90 kg or ≥90 kg) to compare the survival functions between the dosing groups. The hazard ratios for these comparisons for the variable and their corresponding 95% confidence intervals will be computed using a stratified, Cox proportional hazards regression model with dosing group and baseline PASI as explanatory variable and stratified by country and weight at Week 24. The SAS procedure PHREG, with option STRATA if applicable, will be used to perform the analysis. The Kaplan-Meier estimates of the survival functions for each treatment will be plotted. The plot will include the number of subjects at risk for each treatment group at pre-specified timepoints (e.g., visits). Median time to event and quartiles including 95% confidence intervals will be provided. The confidence intervals will be based on log-log transformation. (PROC LIFETEST option conftype=log-log; default in SAS 9.2). In addition, for pre-specified time intervals the following will be presented in an output:

for each treatment group and time interval: subjects at risk, subjects with event, subjects with event divided by subjects at risk, cumulative subjects with event and cumulative event probability including 95% confidence interval

The pre-specified time intervals for Treatment Period 2 are as follows: "\( \leq 4 \) weeks", "\( > 4 \) weeks to  $\leq 8$  weeks", ">8 weeks to  $\leq 12$  weeks", ">12 weeks to  $\leq 16$  weeks", ">16 weeks to ≤20 weeks", ">20 weeks to ≤24 weeks", ">24 weeks to ≤28 weeks" and ">28 weeks".

Subjects at risk, timepoint "0" and censoring will be defined as described in Table 2-1 below.

Table 2-1	i ime to	event: defin	ition of risk se	et, timing an	a censoring i	by variable
Variable: Time to	Risk set	Time = 0	Time of event	Censoring	Psoriasis ConMed	Informative censoring
PASI 90 response	FAS-P75R	Date of randomi- zation (Week 24)	Date of 1 st visit with PASI 90 response observed	End of Treatment Period 2 (Week 52 visit)	Censor (if ConMed taken before the event)	No

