Loss of PASI 90 response	FAS-P90R	Date of randomi- zation (Week 24)	Date of 1 st visit with OBSERVED loss of PASI 90 response (i.e. no imputation for missing values)	End of Treatment Period 2 (Week 52 visit)	Event (if the subject took psoriasis ConMed, the subject is considered as having lost response)	Study phase discontinu- ation with reason "lack of efficacy"
Loss of PASI 75 response	FAS-P75R	Date of randomi- zation (Week 24)	Date of 1 st visit with OBSERVED loss of PASI 75 response (i.e. no imputation for missing values)	End of Treatment Period 2 (Week 52 visit)	Event (if the subject took psoriasis ConMed, the subject is considered as having lost response)	Study phase discontinu- ation with reason "lack of efficacy"
Loss of IGA mod 2011 0 or 1 response	- All IGA 0 or 1 responders at Week 24 in FAS- P90R - All IGA 0 or 1 responders at Week 24 in FAS- P75R	Date of randomi- zation (Week 24)	Date of 1 st visit with OBSERVED loss of IGA mod 2011 0 or 1 response (i.e. no imputation for missing values)	End of Treatment Period 2 (Week 52 visit)	Event (if the subject took psoriasis ConMed, the subject is considered as having lost response)	Study phase discontinu- ation with reason "lack of efficacy"

ConMed: Concomitant medication

Psoriasis ConMed is defined in MAP appendix

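### SAP 1.7 places every incomplete medication date before first dose, even when the known year or month falls after it

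*SAP*

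**What the plan says.** SAP section 1.7 (Prior and concomitant medication) contains four rules that interact.

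- Prior: "Prior medications are defined as drugs taken and stopped prior to first dose of study treatment".
- Concomitant: "Any medication given at least once between the day of first dose of study treatment and the last day of Treatment Period 2", including drugs begun before baseline and continued.
- No end date: "Medication with start date prior to Baseline and without end date will be considered as concomitant medication".
- Incomplete dates: "Incomplete start and/or stop dates (e.g. only the year) of medication are supposed to lie before the date of first dose of study treatment".

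The last rule covers all medication and gives a year-only date as its example. Nothing limits it to cases where the known part of the date is compatible with the period before first dose. Protocol section 9.3.1 defines prior and concomitant medication in much the same way and has no rule for partial dates. SAP section 1.1.1, which lists changes from the protocol methods, does not mention one.

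SAP section 2.3, Table 2-1, uses psoriasis medication in the time-to-event analyses. For the three loss-of-response variables it counts as an event ("if the subject took psoriasis ConMed, the subject is considered as having lost response"). For time to PASI 90 response the entry is "Censor (if ConMed taken before the event"). The table note adds: "Psoriasis ConMed is defined in MAP appendix".

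**The concern.** The rule discards information that the record contains. The protocol's amendment rationale says: "The first patient was recruited in the study on 12 June 2015". Treatment lasts 52 weeks, so patients first dosed in 2015 are treated into 2016. For such a patient, a drug recorded with start 2016 and stop 2016 cannot precede first dose, yet the sentence puts it there and the drug becomes prior. That conflicts with the same section's definition of concomitant medication, which requires only one administration on treatment.

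The rule also reverses the weight of evidence. A drug started before baseline with no end date is concomitant. Add a stop year of 2016, which shows that use continued on study, and the drug becomes prior.

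At stake are the concomitant-medication tables. SAP 1.7 splits these by period: Treatment Period 1 for SAF-TP1, and Treatment Period 2 for FAS-P90R and FAS-P75R. A misplaced onset can therefore also put a drug in the wrong period.

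**Working it through.** No sample size, power or margin is involved, so the plan has no figure to reproduce. The check is to apply the SAP 1.7 rules literally to a drug that was in fact used on study.

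Take first dose as day 0. Let a complete pre-dose start be day −100, a complete on-study start day 200 and a complete on-study stop day 250. Any partial date is set to day −1, that is, before first dose. Then:

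- a missing stop makes the drug concomitant;
- a stop earlier than the start is a contradiction;
- otherwise, stop < 0 gives prior and stop ≥ 0 gives concomitant.

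Three kinds of start and three kinds of stop give 3 × 3 = 9 patterns.

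| Start | Stop | Partial date? | Result |
|---|---|---|---|
| Complete, pre-dose | Complete, on study | no | concomitant (correct) |
| Complete, pre-dose | Missing | no | concomitant (correct) |
| Complete, on study | Complete, on study | no | concomitant (correct) |
| Complete, on study | Missing | no | concomitant (correct) |
| Complete, pre-dose | Partial | yes | **prior (wrong)** |
| Partial | Partial | yes | **prior (wrong)** |
| Complete, on study | Partial | yes | **contradiction: stop −1 before start 200** |
| Partial | Complete, on study | yes | concomitant, but start placed before first dose |
| Partial | Missing | yes | concomitant, through the no-end-date rule |

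Five of the nine patterns contain a partial date. Of these, 2 are filed as prior, 1 has no consistent result and 2 stay concomitant. In the contradictory pattern, the given-at-least-once definition points to concomitant, but the imputed stop does not.

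The deciding element is the stop date, because a drug is prior only if it also stopped before first dose. Filing on-study use as prior therefore needs a partial stop together with a partial or pre-dose start.

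Reach, section by section:

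- **SAP 1.7 tables:** directly affected.
- **SAP 1.8.3, primary and key secondary PASI 90 response:** based on the observed Week 52 PASI, with missing counted as non-response. Medication dates do not enter.
- **SAP 2.3, Table 2-1:** psoriasis medication matters here, but its definition is in an appendix that was not supplied. The documents do not say that the SAP 1.7 dates are used. SAP Table 1-5 classes these variables as exploratory.
- **SAP 1.2, per-protocol set:** based on selected deviations and a data review, not on the prior/concomitant label.

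**The case against.** The strongest reply is that the rule is a reasonable default and does little harm. Protocol Table 5-2 requires washout of earlier psoriasis therapies, and Protocol 5.5.7 collects therapy used before Day 1 on its own eCRF page. Many year-only dates could therefore belong to treatments that really had stopped. Setting every partial stop to its latest possible date would turn a therapy stopped in 2015, in a patient first dosed late in 2015, into apparent on-study psoriasis treatment. In addition, concomitant medication is reviewed at every visit (Protocol Table 6-1), and eCRF entries are queried for completeness (Protocol 8.3).

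This stands for ambiguous dates. Where the known year or month is compatible with the period before first dose, a pre-dose default is defensible. It does not rescue the rule where the known part rules that period out, and data queries do not change how the dates that remain partial are handled.

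Three stronger readings are tempting, and the documents do not support them.

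- A reader might infer that any incomplete start or stop date makes a drug prior. A partial start alone does not, as the table shows.
- A reader might infer that the section always resolves doubt towards no on-study use. Where the partial-date sentence changes the classification, it does move the drug to prior, but the no-end-date sentence in the same section works the other way.
- A reader might infer that loss of response is under-counted, or that prohibited use is hidden from the per-protocol review. Neither Table 2-1 nor the deviation process is stated to use these dates. Protocol 5.5.8 requires prohibited treatment to be recorded, SAP 1.5.1 takes reportable deviations from a separate edit-check specification, and an observed loss of response remains an event in Table 2-1 whatever the medication date.

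**Conclusion.** The sentence is faulty as written. It produces impossible dates and contradicts the section's own definition of concomitant medication. Two of the five partial-date patterns for a drug used on study are misfiled as prior, one contradicts itself, and a partial start with an on-study stop has its onset wrongly placed before first dose whenever the true start was later.

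The consequence that can be shown is error in the concomitant-medication tables. An effect on the exploratory time-to-event analyses is conditional on Table 2-1 using the same dates. The primary and key secondary analyses are unaffected.

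The number of records cannot be computed. A reader might assume that 5% of the 1140 patients planned for Groups 1 and 2 use psoriasis medication on study and that 10% to 20% of those records have partial dates: 1140 × 0.05 × 0.10 = 5.7 and 1140 × 0.05 × 0.20 = 11.4. Neither rate has a source in the documents. The product also treats every partial date as misfiled and every misfiled record as a lost event, so it should not be used as an estimate. This is a minor point, but a clear correction.

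**What to change.** Amend the incomplete-date sentence in SAP 1.7 along these lines:

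- Place an incomplete start or stop date before first dose only if the known year or month, and any complete start date, allow it.
- Otherwise, impute the date within the known month or year, with a stop never earlier than the start, and classify the drug as concomitant.
- Assign the drug to Treatment Period 1 or 2 on the same basis.
- State whether Table 2-1 uses these dates.

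This keeps the pre-dose default for ambiguous dates, so washed-out therapies with only a year recorded are not turned into on-study treatment where that year allows a pre-dose stop. The cost is one amended passage and slightly more programming.

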#### 1.8 Efficacy evaluation

#### 1.8.1 Variables

The primary efficacy variable is the maintaining of PASI 90 response at Week 52 for patients with PASI 90 response at Week 24. The primary analysis of this primary variable will be based on the FAS-P90R.

Table 1-5 lists the primary, key secondary, secondary and exploratory variables for this study. The testing strategy for the analysis of the primary variable is described in Section 1.8.6.

\*: number of treatment (e.g. two treatment cycles with the same medication are counted twice)

\*\*: at least one therapy with lack of efficacy or lack of tolerability

Table 1-5 Primary, key secondary, secondary and exploratory efficacy variables as described in the protocol by treatment period

Variable	Туре	Treatment Period
PASI 90 response at Week 52 for patients with PASI 90 response at Week 24	primary	TP2
PASI 90 response at Week 52 for patients with PASI 75 response but without PASI 90 response at Week 24	key secondary	TP2
PASI 50/75/100 response at Week 52	secondary	TP2
IGA mod 2011 0 or 1 response at Week 52	secondary	TP2
Time course of PASI from Week 24 to Week 52 and change of PASI compared to baseline 	secondary	TP2/FU 
Time course of DLQI from Week 24 to Week 52 and change of DLQI compared to baseline	secondary	TP2
Time course of DLQI 0 or 1 from Week 24 to Week 52	secondary	TP2
Time course of EQ-5D-5L from Week 24 to Week 52 and change of EQ-5D-5L compared to baseline	secondary	TP2
Time course of WPAI-PSO from Week 24 to Week 52 and change of WPAI-PSO compared to baseline	secondary	TP2
Time course of assessment of pain itching and scaling from Week 24 to Week 52 and change of this assessment compared to baseline	secondary	TP2
PASI 50, 75, 90 and 100 response at Week 24	exploratory	TP1
IGA mod 2011 0 or 1 response at Week 24	exploratory	TP1
Time to PASI 90 response from Week 24 on for patients with PASI 75 response but without PASI 90 response at Week 24	exploratory	TP2
Time to loss of PASI 75 response from Week 24 on for patients with PASI 75 response but without PASI 90 response at Week 24	exploratory	TP2
PK data and PASI response during course of the study	exploratory	TP1/TP2
Time to loss of PASI 90 response after Week 24 for patients with PASI 90 response at Week 24	exploratory	TP2
Time to loss of IGA mod 2011 0/1 response after Week 24	exploratory	TP2

1: for patients in the FAS-P75R also the Week 60 visit will be considered for this analysis

Additional efficacy endpoints not described in the protocol but included in the analysis are listed in Table 1-6.

Table 1-6 Additional efficacy variables not described in the protocol by treatment period

Variable	Туре	Treatment Period
PASI 50/75/90/100 response from Week 24 to Week 48 	additional secondary	TP2/FU 
IGA mod 2011 0 or 1 response from Week 24 to Week 48 	additional secondary	TP2/FU 
Body Surface Area affected by plaque-type psoriasis at Week 52 and change from baseline	additional exploratory	TP2
Time course of PASI from Baseline to Week 24 and change of PASI compared to baseline	additional exploratory	TP1
PASI 50/75/90/100 response from Week 1 to Week 20	additional exploratory	TP1
IGA mod 2011 0 or 1 response from Week 1 to Week 20	additional exploratory	TP1
Time course of DLQI from Baseline to Week 24 and change of DLQI compared to baseline	additional exploratory	TP1
Time course of EQ-5D-5L Baseline to Week 24 and change of EQ-5D-5L compared to baseline	additional exploratory	TP1
Time course of WPAI-PSO from Baseline to Week 24 and change of WPAI-PSO compared to baseline	additional exploratory	TP1
Time course of assessment of pain, itching and scaling from Baseline to Week 24 and change of this assessment compared to baseline	additional exploratory	TP1
Relapse at Week 60	additional exploratory	FU
Rebound at Week 60	additional exploratory	FU

1: the analysis of this variable will be added to the respective analysis for Week 52

An overview of statistical analyses and methods applied to efficacy variables is given in Table 1-7

2: for patients in the FAS-P75R also the Week 60 visit will be considered for this analysis

